4.2 Protocol Deviations

A protocol deviation is any noncompliance with the clinical trial protocol or International Council on Harmonization Good Clinical Practice (ICH GCP). The noncompliance may be either on the part of the participant, the investigator, or the study site staff. As a result of deviations, corrective actions are to be developed by the site and implemented promptly.

It is the responsibility of the site investigator to use continuous vigilance to identify and report deviations. All deviations must be addressed in study source documents and entered into the IBM Clinical Development system. Protocol deviations must be sent to the reviewing Institutional Review Board (IRB) per their policies. The site investigator is responsible for knowing and adhering to the reviewing IRB requirements.

All protocol deviations will be listed.

5 DATA HANDLING

5.1 Computing Environment

All descriptive statistical analyses will be performed using SAS statistical software (Version 9.4 or later), unless otherwise noted. Medical comorbidities and adverse events will be coded using the Medical Dictionary for Regulatory Activities (MedDRA) version 24.0 or later. Prior and concomitant medications will be coded using World Health Organization (WHO) Drug version Global B3 (March 2021 or later). The actual version of the dictionary used will be noted in the footnote of the respective output.

5.2 Data Conventions

The following conventions will be used:

- **Period definition:**
 - **Screening Period:** The period prior to the date of first dose of study drug (Day 0)
 - **On-Treatment Period:** The period from date of first dose of study drug through the Week 24 study visit
- **Study day 0:** The date of first dose of study drug
- **End of Treatment Visit:** End of treatment/early withdrawal visit
- **End of Study Visit:** The last recorded visit date
- **Unscheduled or repeated visits:** Unscheduled visits results will be listed, but not included in tables or graphs.
- **Conversion factors:**
 - 1 month = 30.4375 days
 - 1 year = 365.25 days
 - 1 week = 7 days
 - °C = (°F - 32)/1.8
- **Additional rules**
 - Age (years) = (date of informed consent – date of birth + 1) / 365.25, rounded to the lowest whole number.
 - Weight values recorded in pounds will be converted to kilograms using the following formula: kilograms = pounds/2.2046.
 - Height values recorded in inches will be converted to centimeters using the following formula: centimeters = inches*2.54.

- Duration on study (weeks) = (Last visit date – randomization date + 1) / 7.
- Duration on treatment (weeks) = (Last study drug intake date – first study drug intake date + 1) / 7.
- (Absolute) Change from baseline = Value at the time point – Baseline value.
- Relative change from baseline = [(Value at the time point – Baseline value) / Baseline value] x 100.

5.3 Methods of Pooling Data

Not applicable.

5.4 Withdrawals, Dropouts, Loss to Follow-up

Discontinued subjects will not be replaced whether they received or did not receive the study drug. The multiple imputation approach is included in Section 6.4.

Follow-up of subjects who discontinued the study drug early will continue until Week 24 and the study procedures will be assessed as per the schedule of assessment (see Table 9-1).

5.5 Visit Windows

All visits (scheduled, unscheduled or withdrawal) will be mapped to an analysis visit as defined in Table 5-1, where Day 0 is defined as the date of first dose of study treatment. All safety and efficacy analyses will be based on the analysis visit. In cases where a subject has more than one particular analysis visit, the visit with non-missing data closest to the protocolled visit will be selected for analysis.

Table 5-1: Evaluation Intervals for Efficacy Analysis

Scheduled Visit	Protocol-Specified Interval	Interval for Analysis Visit
Baseline	Day –14 to Day –1	Day –14 to Day -1
Week 12	Day 77 to Day 91	Day 0 to Day 125
Week 24	Day 161 to Day 175	Day 126 to Day 175

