6.6.2 Laboratory Data

Safety laboratory data at each study visit and changes from baseline will be summarized by treatment group. Laboratory parameters will be reported in original units without conversion, see Table 9-2.

In addition, clinical laboratory summaries will be presented by treatment group including: (i) incidence of significant abnormalities by visit; (ii) tables summarizing the frequencies of subjects below, within, and above the normal reference ranges at baseline and end of study; and (iii) tables displaying baseline to end of study shifts in each laboratory value (shifts between below, within or above normal range).

All laboratory data will be provided in data listings.

A subset listing will be presented for all abnormal laboratory values.

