9 APPENDICES

9.1 Schedule of Assessments

Table 9-1: Schedule of assessments

	Baseline	Randomization	Phone Visit Week 4	Week 12	Week 24	
Visit #	1	Non-visit	PH	2	3	
Day #	-14 to -1	-1	0	28 ± 7	84 ± 7	168 ± 7
Inclusion/Exclusion Criteria	X					
Informed Consent	X					
History and physical exam						
Demographics	X					
Medical history	X					
Symptom assessment	X			X	X	
Concomitant medications	X			X	X	
Vital Signs & Weight	X			X	X	
Physical Examination	X			X	X	
Safety laboratories						
Laboratory Draw	X				X	
Comprehensive metabolic panel	X				X	
Complete blood count	X				X	
Mass-Spectrometry for H ₂ antagonists	X				X	

Pregnancy test if premenopausal	X				X
Endpoint assessment					
6 minute-walk distance (primary)	X			X	X
echocardiogram	X				X
emPHasis-10 score	X			X	X
BNP	X				X
NYHA functional class	X			X	X
Study Procedures					
Dispense study drug		X		X	
Start study drug			X		
Study drug adherence				X	X
Study drug compliance				X	X
Adverse events	X			X	X
Study Termination					X
Sub-study components					
Right heart catheterization (n=20)	X				X
Cardiopulmonary Exercise Test (n=10)	X				X
Miscellaneous					
Data Safety Monitoring Board			Semi-annually		

As per clinical practice guidelines, patients will be seen every three months with blood work and six-minute walk testing. These elements (visit, laboratory draw, comprehensive metabolic panel, complete blood count, BNP, pregnancy test, 6 minute-walk distance, and NYHA functional class) will be collected as part of routine medical care and abstracted from the medical record as research endpoints. Echocardiograms are often part of routine medical care and will be abstracted from the medical record as research endpoints; however, the frequency may be influenced by the study. To avoid any concern about overlap, any

echocardiogram occurring more frequently than annually will be considered research. It is anticipated that 1 of the 2 echocardiograms will fit this research definition. Other research elements include mass spectrometry for H2 antagonists, the emPHasis-10 score, study procedures, and sub-study components.

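### When two laboratory draws share an analysis window, the closest-visit rule in SAP 5.5 can drop an abnormal value, and no any-time or worst-value table recovers it

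*SAP*

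**What the plan says.** - **SAP 5.5** opens with "All visits (scheduled, unscheduled or withdrawal) will be mapped to an analysis visit as defined in Table 5-1" and continues "All safety and efficacy analyses will be based on the analysis visit". If a participant has more than one visit in a window, "the visit with non-missing data closest to the protocolled visit will be selected for analysis". The Week 12 window is "Day 0 to Day 125" and the Week 24 window is "Day 126 to Day 175". The table holding these windows is titled "Evaluation Intervals for Efficacy Analysis", which does not match the safety scope given in the text above it.
- **SAP 5.2** sends results from unscheduled or repeated visits to listings only. It defines end of study by the last recorded visit.
- **SAP 6.6.2** plans, by arm: values and changes at each visit; (i) "incidence of significant abnormalities by visit"; (ii) frequencies below, within and above the normal range at baseline and end of study; and (iii) shifts from baseline to end of study. All laboratory data are listed, and abnormal values have a separate listing.
- **SAP 5.4** keeps participants who stop study drug early in follow-up to Week 24, with the scheduled procedures.
- **Protocol 1.3 and SAP Table 9-1** place the only post-baseline safety draw at Week 24. SAP 9.1 adds that "patients will be seen every three months with blood work and six-minute walk testing", whereas Protocol 1.3 gives three to six months. Both say that these routine results are abstracted as research data.

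**The concern.** Choosing the value nearest a target day is sensible for a mean at a visit, where one comparable value per participant is wanted. It does not suit a count of abnormalities. There the question is whether a participant had one at all, and the day on which it was found should not decide whether it counts. Under SAP 5.5 a normal value nearer Day 84 or Day 168 replaces an abnormal one further away, and table (i) then counts only the selected value. Tables (ii) and (iii) look only at the two ends of the study, so they do not bring the earlier value back.

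What is at stake is the completeness of the by-arm laboratory comparison. Protocol 2.1 names safety assessment as an aim, and with about 40 participants per arm a few missing cases could alter the table.

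**Working it through.** **1. The plan's windows.** Protocol 8.1 sets Week 12 at Day 84 ± 7 and Week 24 at Day 168 ± 7. This gives 77 to 91 and 161 to 175, as in Table 5-1. The midpoint is (84 + 168)/2 = 126, which matches the 125/126 boundary. The Week 12 window spans 126 days (0 to 125) and the Week 24 window 50 days (126 to 175).

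**2. Earlier draw followed by an in-window Week 24 draw.** The later draw replaces the earlier one when its distance from Day 168 is smaller.
- Draw on Days 126 to 160: the distance is 168 − 160 = 8 at least and 168 − 126 = 42 at most.
- Week 24 draw on Days 161 to 175: the distance is at most 7.
- Since 8 > 7, the earlier value is always replaced. That is 160 − 126 + 1 = 35 of 50 days.

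**3. Abnormal Week 24 draw repeated r days later.** With the first draw on day d, the repeat replaces it when |d + r − 168| < |d − 168|, with d + r no later than 175.
- r = 7: true for d = 161 to 164, so 4 of the 15 window days.
- r = 3: true for d = 161 to 166, so 6 of 15.

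**4. All ordered pairs of draw days within a window.**

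| Window | Pairs | Earlier replaced | Tied | Earlier kept |
|---|---|---|---|---|
| Week 12 | 7875 | 6153 (78%) | 41 | 1681 |
| Week 24 | 1225 | 1169 (95%) | 7 | 49 |

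The Week 12 row needs two extra draws, since none is scheduled in that window.

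**5. One extra draw before the Week 24 protocol window (Days 0 to 160, 161 days), followed by an in-window Week 24 draw.** Under 5.5, a draw on Days 0 to 125 is kept as the Week 12 value (126 of 161) and one on Days 126 to 160 is replaced (35 of 161). Under 5.2, if the draw counts as unscheduled, it is tabulated on none of the 161 days.

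All of these are counts of days. They are not probabilities, because the documents give no distribution of extra draws.

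**6. Where a second draw could come from.**
- A draw at early withdrawal on Days 126 to 160, followed by the Week 24 draw under SAP 5.4. SAP 5.2 lists early withdrawal as its own visit type, so its exclusion of unscheduled visits does not clearly reach it. Table 9-1 has no withdrawal column, so that blood is drawn there is an assumption.
- The catheterization sub-study (n = 20 of about 80). Protocol 8.1 has bloodwork checked on the day of the procedure, within 7 days of the Week 24 visit. This matters only if the results enter the database, which is not stated.
- Routine-care blood work, or a repeat of an abnormal result.

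**The case against.** Much of the opposing case stands.

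- **The loss is conditional.** Only one post-baseline safety draw is scheduled. Without a second draw in the same window, nothing is displaced. A participant who leaves the study after a draw on Days 126 to 160 keeps that value under 5.5, because no later one exists.
- **The repeat-draw counts depend on which section governs.** If SAP 5.2 applies, an unscheduled repeat cannot replace an abnormal Week 24 value, and the 4 of 15 and 6 of 15 become zero. Even under 5.5 the first value survives a 7-day repeat on 11 of 15 days.
- **SAP 5.5 is not the only cause.** Tables (ii) and (iii) leave out earlier values by design. All three tables come from Protocol 9.4.4, which has no closest-visit rule. Table (i) is openly a by-visit table and does not claim to be an any-time incidence.
- **There is another by-arm route.** Protocol 8.2.1 counts an abnormal laboratory finding as a possible adverse event, and the severity grades in 8.2.3.1 mention laboratory alterations. SAP 6.6.1 tabulates treatment-emergent events by arm according to onset, not by a selected visit.

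A reader might infer that a displaced abnormality disappears from every by-arm result, or that the tables are known to understate abnormality rates. The documents do not support either. The adverse event route is open, and the number of extra draws is unknown.

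The objection does not supply a complete laboratory count. The listing gives no comparison by arm. The adverse event route depends on someone reporting the value as an event, which is not the same as applying one laboratory criterion to every result.

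**Conclusion.** The point holds as a conditional gap. Where two draws share an analysis window and the later one is nearer the target day, SAP 5.5 removes the earlier value from the by-visit abnormality table, and no other by-arm laboratory table restores it. The clearest case is a withdrawal draw on Days 126 to 160 followed by an in-window Week 24 draw, where replacement is certain. Following SAP 5.2 does not close the gap: it protects the scheduled Week 24 value but leaves every unscheduled result untabulated, including a lone one on Days 0 to 125 that 5.5 would keep.

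The number of participants affected cannot be estimated from the documents. The conclusion rests on two assumptions: that some extra draws occur, and that their results are entered in the database. It is worth correcting because the data would already be in hand and the two sections contradict each other in any case.

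**What to change.** - Reconcile SAP 5.2 with 5.5 on unscheduled, repeat and withdrawal results, and bring the title of Table 5-1 into line with the scope actually intended.
- In SAP 5.5, limit the closest-visit rule to efficacy variables and to by-visit means and changes.
- In SAP 6.6.2, add a by-arm count of participants with any significant post-baseline laboratory abnormality and a baseline-to-worst shift table. Both should use all scheduled, unscheduled, repeat and withdrawal values. Section 6.6.2 gives no criterion for a significant abnormality, so one should be stated before unblinding. The existing by-visit and end-of-study tables can stay.

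The cost is a few sentences in the SAP and minor programming, with no new visits or samples. Reported abnormality rates would be somewhat higher in both arms, and the text should say that the any-time count is not comparable with the by-visit one.

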6 STATISTICAL METHODS

6.1 Sample Size Justification

The primary endpoint is the change in six-minute walk distance (6MWD). The study was powered to detect a difference of 31.9 meters. A 31.9 meter improvement in 6MWD is well aligned with established thresholds for a minimally important difference in patient reported outcomes (Mathai SC, et al. Am J Respir Crit Care Med, 2012; 186(5):428-433). The 6MWD was chosen because it is a surrogate for patient-centered outcomes and was the primary endpoint in labeling trials for most of the medications used to treat pulmonary arterial hypertension (PAH).

Standard deviation in 6MWD among PAH participants with NYHA functional class II, III, or IV symptoms is 37.6 meters (national Pulmonary Hypertension Association Registry; unpublished data). As shown, the proposed sample size has adequate power (0.96) to detect a minimally important difference in 6MWD even with 10% attrition in the study sample (power, 0.94).

Table 6-1: Power to detect a minimally important difference in 6MWD (31.9 meters)

Alpha	Sample size per group	Power for the total sample size	Sample size per group with ~10% attrition	Power with attrition
0.05	20	0.74	18	0.69
0.05	40	0.96	36	0.94
0.05	60	0.99	54	0.99

The field is appropriately shifting toward larger event driven trials; however, we did not feel a larger event driven trial of famotidine was warranted at this juncture. The current proposal is the first randomized evaluation of this drug and this pathway in individuals with right heart failure and/or PAH and a smaller Phase II trial was felt to be a more appropriate next step.

For the RHC sub-study, the initial sample size was set at 10 participants based on the following power to detect large differences.

Size of difference	SV index (mL/m2)	Total sample size	n per group	power
Large	20	10	5	0.87
Medium-high	15	10	5	0.67
Medium-low	10	10	5	0.36
Small	5	10	5	0.13

For the exercise sub-study, the initial sample size was set at 10 participants based on the following power to detect large differences.

Size of difference	VO2 (mL/min/kg)	Total sample size	n per group	power
Large	8	10	5	0.96
Medium	4	10	5	0.46
Low	2	10	5	0.15

6.2 General Statistical Methods

6.2.1 General Methods

All outputs will be incorporated into Microsoft Excel or Word files, sorted and labeled according to the International Conference on Harmonization (ICH) recommendations, and formatted to the appropriate page size(s).

Tabulations will be produced for appropriate demographic, baseline, efficacy and safety parameters. For categorical variables, summary tabulations of the number and percentage within each category (with a category for missing data) of the parameter will be presented. For continuous variables, the mean, median, standard deviation, minimum and maximum values will be presented.

Formal statistical hypothesis testing will be performed with all tests conducted at the 2-sided, 0.05 level of significance. Summary statistics will be presented, as well as 95% confidence intervals on selected parameters, as described in the sections below.

6.2.2 Definition of Baseline

Baseline is defined as the last non-missing assessment prior to the first dose of study treatment. On the day of randomization all participants will be randomized, and study drug will be dispensed at this visit. Participants will be instructed to take one tablet daily (20 mg of famotidine or placebo) the day following randomization and dispensing of the study drug. All baseline assessments need to be completed within 14 days prior to the start of study drug (not inclusive of the date the first dose of study drug is taken). The day study drug is taken will be considered day 0. See Section 5.5 for details of the visit window for baseline.

6.2.3 Adjustments for Covariates

Subject randomization will be stratified by NYHA/WHO Functional Class (NYHA/WHO Functional Class II versus Class III/IV) to ensure balanced representation of this important marker of severity.

For continuous outcome variables, baseline values of the dependent variable and NYHA functional class (as a binary stratification variable) will be included in the statistical model .

6.2.4 Multiple Comparisons/Multiplicity

No adjustments for multiplicity will be made.

6.2.5 Subgroups

No subgroups analyses are planned.

6.2.6 Missing, Unused, and Spurious Data

The handling of intercurrent events (ICEs) and sensitivity analyses are described in Section 6.4. No other imputation of missing efficacy endpoints will be used.

In all listings, missing or incomplete dates in safety data will be left as they have been recorded. However, for calculation and sorting based on dates and for consideration in summary tables, the following method will be used:

For partial or missing adverse event (AE) start dates the following imputation will be applied:

1. If year is not missing and is after the year of first dose:
 - a. If month is missing, then month will be imputed as January.
 - b. If day is missing, then day will be imputed as the first of the month.

2. If year is not missing and is the same as the year of the first dose:
 - a. If month is missing, then impute the month as the month of the first dose date.
 - b. If day is missing, and the month is the same as the month of the first dose date, then impute day as the day of the first dose date.
 - c. If day is missing but month is after the month of first dose date, then impute day as the first day of the month.
3. If year is missing then impute the year as the year of the first dose date:
 - a. If month is missing, then impute the month as the month of the first dose date.
 - b. If day is missing, then impute the day as the day of the first dose date.
4. If the start date is completely missing, but the AE is either ongoing or the stop date is after the first dose date then impute the start date as the first dose date.
5. For any cases involving the rules above, if the AE end date is before the AE start date, then do not impute the AE start date and assume that the AE is treatment emergent for the purpose of the analysis. Further, if the AE stop date occurs prior to the first dose date, do not impute the AE start date, and assume that the AE is not treatment emergent.

No imputations will be applied to AE stop dates.

A missing/incomplete date of medical comorbidities or disease diagnosis will be assumed to have occurred before any study treatment.

Missing AE relationship data will be assigned the 'related' category for treatment emergent AE.

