8.2.4 TIME PERIOD AND FREQUENCY FOR EVENT ASSESSMENT AND FOLLOW-UP

The study team will record all reportable events with start dates occurring any time after informed consent is obtained until 7 (for non-serious AEs) or 14 days (for SAEs) after the last day of study participation. AEs are identified at any of the three in-person visits, during a phone visit, during a study-based procedure (e.g. heart catheterization or cardiopulmonary exercise test) or when notified outside of the normal visit structure by a participant or surrogate. Events will be followed until resolution or stabilization.

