6.6.1 Adverse Events

Adverse events (AEs) will be coded using the Medical Dictionary for Regulatory Activities (MedDRA), see Section 5.1, and displayed in tables and listings using System/Organ/Class (SOC) and Preferred Term (PT).

Analyses of adverse events will be performed for those events that are considered treatment emergent, where treatment emergent is defined as any adverse event with onset after the administration of study medication through the end of the study (see Section 5.2) or any event that was present at baseline but worsened in intensity or was subsequently considered drug-related by the investigator through the end of the study.

Adverse events are summarized by subject, therefore, in any tabulation, a subject contributes only once to the count for a given adverse event (SOC or preferred term).

The number and percentage of subjects with any treatment-emergent adverse event (TEAE), any treatment-emergent adverse event by severity, with any treatment-emergent adverse event by relationship to study drug, with any treatment-emergent adverse event leading to withdrawal from study drug, and with any treatment-emergent serious adverse event (SAE) will be summarized by treatment group and overall. In these tabulations, each subject will contribute only once (i.e., the most related occurrence or the most intense occurrence), regardless of the number of episodes. The number of events and the average number of events will also be provided in tabulations of TEAEs and serious TEAEs.

Adverse events with definite, probable, and possible relationship are considered related to study drug. Adverse events with unrelated and unlikely relationship are considered unrelated to study drug.

Histograms showing the frequency of the number of treatment-emergent AEs and SAEs in each treatment group will be included.

Exposure-adjusted event rates by treatment group and overall will be provided for participants with TEAEs, and with serious TEAEs. Each summary will present by decreasing incidence of PT per 100 subject years of exposure, calculated as (number of subjects with event/total patient-years). Years of exposure is either a) time from first treatment until start date of TEAE type or b) duration of exposure for subjects without a TEAE type. Poisson regression modeling will be used to derive rate ratios and 95% CIs for each SOC. Rate ratios will be compared using a two-sided 0.05 level test for Poisson count data.

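### SAP 6.2.6 rule 3 dates a new-year adverse event with a recorded month and a missing year 5 to 12 months before first dose, and so before consent

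*SAP*

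**What the plan says.** SAP 6.2.6 sets the rules for incomplete AE start dates.

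- **Rule 3 (year missing):** "If year is missing then impute the year as the year of the first dose date". Its first sub-rule adds "If month is missing, then impute the month as the month of the first dose date", and the second treats a missing day in the same way. Both act only on a part of the date that is missing, so a recorded month or day is kept.
- **Rule 4:** applies "If the start date is completely missing, but the AE is either ongoing or the stop date is after the first dose date", and then uses the first dose date.
- **Rule 5:** "if the AE end date is before the AE start date, then do not impute the AE start date", and the event is then assumed treatment-emergent. Its second sentence makes an event not treatment-emergent if it stopped before first dose.

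SAP 6.6.1 limits the AE analyses to treatment-emergent events. In the first limb, "treatment emergent is defined as any adverse event with onset after the administration of study medication through the end of the study". The second limb adds "any event that was present at baseline but worsened in intensity or was subsequently considered drug-related by the investigator".

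Protocol 8.2.4 defines the recording period for AEs: "start dates occurring any time after informed consent is obtained until 7 (for non-serious AEs) or 14 days (for SAEs) after the last day", where the last day is that of study participation. Protocol 1.2 places consent at the baseline visit, with all baseline assessments in the 14 days before study drug starts. SAP 2.1 gives a screening period of up to 21 days.

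**The concern.** Rule 3 does not test its result against first dose or consent. Participants are followed for about 24 weeks, and a 60-month study lets them start at any time of year, so many will be followed across 1 January. For an event in the new year, the first-dose year is the wrong year. If the month is on the record, the rule pairs a correct month with that wrong year and produces a date from before the participant joined the trial.

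The event then fails the onset limb of the treatment-emergent definition. At stake are the TEAE and serious TEAE counts, the Poisson rate ratios and the hospitalisation comparison. The outcome is also perverse: an ongoing event with no start date at all is placed on the first dose date and kept, while one with a known day and month can be lost.

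**Working it through.** The plan gives no figure for this rule, so there is none to reproduce. The check applies rules 3 to 5 as written.

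**Inputs**
- Last on-study day: 168 + 7 = Day 175 (Protocol 8.1, Week 24 window).
- Latest SAE onset collected: 175 + 14 = Day 189 (Protocol 8.2.4).
- Earliest consent: 14 days before first dose (Protocol 1.2), or 21 days (SAP 2.1).

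**One example.** First dose 1 October 2021; true onset 10 February 2022 (Day 132); year missing. Rule 3 gives 10 February 2021. That is 365 − 132 = 233 days before first dose. It is 233 − 14 = 219 days before the earliest consent, or 233 − 21 = 212 with the longer screening period.

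**All cases, month and day recorded.** For a new-year onset on Day k, rule 3 moves the start back 365 days, so the gap before first dose is 365 − k. The rules were run for every first-dose date in a 365-day year and every onset day. When the day was also missing, rule 3 supplied the first-dose day.

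| Onsets up to | Day of month | Days before first dose | Minimum days before consent (14-day / 21-day) |
|---|---|---|---|
| Day 175 | recorded | 190 to 364 | 176 / 169 |
| Day 175 | missing | 181 to 334 | 167 / 160 |
| Day 189 | recorded | 176 to 364 | 162 / 155 |
| Day 189 | missing | 150 to 334 | 136 / 129 |

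Every new-year onset with a recorded month was dated before first dose. At the SAP's 30.4375 days per month, 150 to 364 days is 4.9 to 12.0 months. Onsets in the same calendar year as first dose were never moved before it.

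**Do the other rules rescue it?** Rule 4 does not apply, because the date is only partly missing. The first sentence of rule 5 needs an end date before the start date, and moving the start back cannot create that; it rescued no case. Its second sentence needs a stop before first dose, which an on-treatment event does not have.

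**Is the true year recoverable?** The collection period is at most 21 + 189 = 210 days. For a calendar month to occur in it twice, it would have to span the eleven months between, at least 365 − 31 = 334 days. The recorded month therefore fixes the year.

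**When the month is also missing.** Rule 3 uses the first-dose month, and the date is at most 30 days before first dose. With nothing recorded, the result is the first dose date.

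**If the second limb keeps the event.** SAP 6.6.1 measures exposure from first treatment to the start of the event. In the example this is −233 / 365.25 = −0.64 years, which is not a valid exposure time.

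**Participants exposed to the rule (assuming starts spread evenly over the year).** On treatment across 1 January: 168/365 = 46%. Followed to Day 175: 175/365 = 48%, or about 38 of 80. On-study days in the new year: (175 × 176 / 2) / (365 × 175) = 15,400 / 63,875 = 24%.

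**The case against.** The best defence is that the pattern should hardly occur. Protocol 10.1.8 sends missing or anomalous data back to the site, and Protocol 10.1.9.1 describes automatic checks for incomplete entries. AEs are gathered at one site at scheduled contacts, so staff who know the month can normally supply the year. A hospitalisation should also have a dated record. This stands as an argument about frequency. It does not defend the rule, which exists for the records that queries leave unresolved.

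A reader might infer more than the documents support:

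- **That any missing year sends a new-year event back by months.** It does so only if the month is recorded.
- **That every such event is certain to leave all AE output.** The second limb can keep an event that worsened or was judged drug-related. SAP 6.2.6 leaves listing dates as recorded, and SAP 6.6.1 lists all on-study AEs, with separate listings of deaths, SAEs and hospitalisations.
- **That nearly half of events are at risk.** The 46 to 48% counts participants. The share of events affected also depends on how often a month is recorded without a year, which is unknown.
- **That rule 3 reverses a general lean towards treatment-emergent.** Its month and day defaults lean the same way as rule 2, and the second sentence of rule 5 leans the other way. The fault is an unhandled year boundary.

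**Conclusion.** Rule 3 is wrong as written for one defined pattern: year missing, month recorded, true onset in the calendar year after first dose. Every such event is dated 150 to 364 days before first dose and at least 129 days before consent, where Protocol 8.2.4 allows no AE to start. It then leaves the treatment-emergent summaries unless the second limb keeps it, and in that case its time to onset is negative. The date ranges follow from the documents' own windows and a 365-day year. The 46 to 48% of participants exposed rests on assumed even enrolment.

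The expected number of affected events is small and cannot be estimated from the documents. This is a minor correction, worth making because it is cheap and because, with about 80 participants, one lost SAE or hospitalisation could show in the comparison between arms.

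**What to change.** Reword rule 3 along these lines:

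> If the year is missing and the month is recorded, impute the year in which the recorded month falls in or after the month of informed consent and within the AE collection period, comparing month and year only when the day is missing. Then impute a missing day by rule 1b, 2b or 2c: the day of first dose if the event falls in the first-dose month, otherwise the first of the month. If the month is also missing, use the first dose date, subject to rule 5.

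Two details matter. The comparison must use month and year alone when the day is absent; otherwise an event in the consent month could not be placed, or could be pushed forward a year. A day rule must also remain, because replacing rule 3 with a year rule alone would leave a month-only record without a full date.

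The cost is one reworded rule and a small change to the date-imputation code, best made before unblinding. It needs no new data.
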